Validation of Serum Assays for the Diagnosis of Gastritis

ClinicalTrials.gov ID: NCT05883345

Document date: May 28, 2023

Main investigator

Name: [name], PhD

Address: [name]

Phone/[contact]

E-mail: [contact]

Number of involved center: 1 (Konkuk University Medical Center)

Title of the study: Validation of Blood Test Finding for the Diagnosis of Gastritis and Gastric Neoplasms

Protocol ID: 2023-04-056

Keywords: *Helicobacter pylori*, Atrophic gastritis, Gastric cancer, Pepsinogen

Rationale of the study

Helicobacter pylori-seropositive rates are decreasing in South Korea. Seroprevalence was 74.3% in 1990, but it decreased to 43.9% in 2016. In Koreans, most gastric cancers are related to *H. pylori* infection. *H. pylori*-negative gastric cancers were found only in 2.3% among the 1,833 Korean gastric cancer patients. Despite these facts, the national guideline still recommends biennial gastroscopy for all Koreans aged between 40 and 75 years. Therefore, 8,462,570 (63.1%) Koreans underwent gastric cancer screening among the target population of 13,404,927 individuals in 2021.

In *H. pylori*-seroprevalent populations, diagnostic criteria for naive status should be strict based on histology, endoscopy, and serum pepsinogen (PG) assay findings. Naive condition should be diagnosed only when both invasive and non-invasive *H. pylori* tests show negative

findings. Furthermore, there should be no intestinal metaplasia and atrophy on serum PG assay, endoscopy, and histology findings in *H. pylori*-naive participants. Based on those findings, *H. pylori* infection will be confirmed when invasive tests or urea breath test was positive. *H. pylori*-naive status will be diagnosed if there was no eradication history, no serologically detected atrophy (PG I \leq 70 ng/mL and PG I/II \leq 3), and no intestinal metaplasia or atrophy on endoscopy and histology.

This study aimed to determine the validity of blood tests for gastric cancer screening according to the *H. pylori* infection status. We tried to identify significant variables using GastroPanel tests and traditional serum PG assays according to the presence gastric neoplasms.

Study design

Study Type	Observational
Observational Study Model	Cohort
Time Perspective	Prospective
Biospecimen Retention	Samples Without DNA
Biospecimen Description	Blood sample
Enrollment	1490 [Actual]

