Primary objective: To determine the validity of blood tests for gastric cancer screening

Endpoints:

- Primary endpoint: Significant blood test findings (*H. pylori* IgG, PG I, PG II, I/II ratio, G-17) indicating the presence of gastric neoplasms
- Secondary endpoint: Test findings according to the types of gastric neoplasms

Expected results: GastroPanel test and conventional serum pepsinogen findings would differ according to the presence and types of gastric neoplasms.

Analyzed criteria: Gastric neoplasms were diagnosed when microscopic findings correspond to the international classification of diseases-10 categories C16, D002, D131, and C1884. Adenocarcinomas (C16 and D002) were further divided into advanced gastric cancers (AGCs) and early gastric cancers (EGCs) after resecting the cancers. Gastric adenomas were confirmed among benign neoplasms of the stomach (D131), after the resection. Following excision of submucosal tumors, neuroendocrine tumors (NETs) and gastrointestinal stromal tumors (GISTs) were verified as C16. Primary gastric mucosa-associated lymphoid tissue (MALT) lymphomas were identified as C1884 using the gastric biopsy specimens.

Main variables/endpoints of the analysis

Age (years)
Male sex
Status of H. pylori infection
GastroPanel test findings H. pylori IgG (EU) PG I (µg/L) PG II (µg/L) I/II ratio Gastrin-17 (pmol/L)
Conventional serum assays (Chorus tests and HBI PG assays) H. pylori IgG (AU/mL) PG I (mg/dL) PG II (mg/dL) I/II ratio

Safety variables: No adverse events during the study period (May 1, 2023 ~ August 30, 2024)

Visits and examinations

Initial visit:

- Blood test for *H. pylori* immunoglobulin G, pepsinogen, and gastrin-17 levels
- Upper gastrointestinal endoscopy and gastric biopsy

Follow-up visit:

- ¹³C-urea breath test if there is a discrepancy between the *H. pylori* test findings

Study population

Short description of the main inclusion and exclusion criteria

Study Population:	Adult population who visited our center for gastric cancer screening using serum assays
Sampling Method:	Non-Probability Sample
Minimum Age:	18 Years
Maximum Age:	99 Years
Sex:	All
Gender Based:	No
Accepts Healthy Volunteers:	No

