Criteria:	
Inclusion Criteria:
 
 • Individuals who visited for gastric cancer screening 
Exclusion Criteria:
 
 • History of gastrectomy • Renal insufficiency • Severe comorbidities requiring prompt management
-----------	--

Sample size and statistical analysis

Prior to the study, sample size calculation was done for the validation of GastroPanel test in Koreans. Briefly, two-sided tests were used at a significance level of 0.05. Using PASS 2023 (NCSS, LLC. Kaysville, Utah, USA), the power was 0.842 when 414 individuals are included.

Chi-square test was used for categorical variables, while t-test was used for continuous variables to compare the differences between the patients with gastric neoplasms and the controls. When the data showed asymmetrical distribution, Fisher's-exact was used to present categorical variables as proportion, while Kruskal-Wallis test was used to present continuous variables as median value with ranges. ANOVA with Bonferroni correction was used to assess differences between the three groups for continuous variables, while chi-square test with Bonferroni correction was used for categorical variables. Thereafter, independent variables for gastric neoplasms were identified using logistic regression analysis. The results are shown as odds ratio (OR) with 95% confidence intervals (CIs). Correlation analysis was used to identify associations between the blood test results and the severity of

atrophy. The results are shown as correlation coefficient (r) values. Furthermore, receiver operating characteristic (ROC) curve analysis was done, and presented as area under the curve (AUC). ROC curves were compared using the McNemar's test. Using PASW statistics (version 28.0; SPSS Inc., Chicago, IL, USA), a p -value less than 0.05 was considered significant.

Duration of the study

Study Start:	May 1, 2023 [Actual]
Primary Completion:	August 30, 2024

Additional features on the main concept of the study

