Serum pepsinogen (PG) assays are another method used to quantify the severity of atrophy, in addition to endoscopic and microscopic measurements. In contrast to traditional serum PG assays, GastroPanel tests incorporate the measurement of gastrin-17 (G-17), a substance exclusively secreted by the gastric antrum. The G-17 level decreases to less than 1 pmol/L following distal gastrectomy or in the presence of antral atrophy, but it increases to 30 pmol/L when corpus atrophy develops. European studies using GastroPanel tests revealed that gastric atrophy can be identified with low G-17 levels of <1 pmol/L. Nonetheless, this metric is difficult to apply in *H. pylori*-seroprevalent areas where corpus atrophy is common. A Chinese study showed that gastric cancer development is linked to both low (<0.5 pmol/L) and high (>4.7 pmol/L) G-17 levels; however, these are less helpful in clinical practice because G-17 levels of >4.7 pmol/L are frequently observed even in the absence of atrophy. Altogether, it is still uncertain whether adding a G-17 measurement to PG assays would contribute to the detection of gastric neoplasms. Hence, we attempted to identify actual blood levels for

detecting gastric neoplasms rather than focusing on identifying high-risk individuals.

Additionally, we tried to confirm the significance of the test results according to the type of gastric neoplasm.

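### The stated aim is the validity of blood tests for cancer screening, yet AUC is the only accuracy measure planned; sensitivity and specificity at cut-offs fixed in advance should be added

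*Combined protocol and SAP*

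**What the plan says.** The primary objective reads "To determine the validity of blood tests for gastric cancer screening". The primary endpoint takes the markers one by one: besides *H. pylori* IgG it names "PG I, PG II, I/II ratio, G-17) indicating the presence of gastric neoplasms".

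The section on sample size and statistical analysis plans group comparisons, logistic regression with odds ratios, correlation with the severity of atrophy, and ROC analysis: "receiver operating characteristic (ROC) curve analysis was done, and presented as area under the curve (AUC". It adds that "ROC curves were compared using the McNemar's test". Sensitivity, specificity and predictive values are not mentioned anywhere.

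The document does give thresholds:

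- The rationale counts as one condition of *H. pylori*-naive status "no serologically detected atrophy (PG I \leq 70 ng/mL and PG I/II \leq 3" (closing bracket omitted).
- The section on additional features says "European studies using GastroPanel tests revealed that gastric atrophy can be identified with low G-17 levels of <1 pmol/L".
- The same section cites a Chinese study that links gastric cancer development to G-17 both below 0.5 and above 4.7 pmol/L. It then calls these limits less useful because "G-17 levels of >4.7 pmol/L are frequently observed even in the absence of atrophy".

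None of these thresholds is scored against neoplasm in the planned analyses.

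**The concern.** Screening acts on a positive or negative result. An AUC says how well a marker ranks people. It does not say how many neoplasms a given rule finds or misses, or how many people without neoplasm it flags. Two features of this document make the gap matter more than usual. Its pepsinogen rule requires two conditions at once, and its cancer-related G-17 limits lie at both ends of the scale. AUCs of single markers settle neither. The study could end with an AUC for each marker and still not report the error rates that a screening programme needs, although the data would allow it.

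**Working it through.** **The plan's own figure.** The stated power of 0.842 with 414 people (two-sided 0.05) cannot be reproduced, because no effect size, test statistic or case share is given. For two means, d = (1.960 + 1.003) × √(1/n₁ + 1/n₀). This gives d = 0.29 with equal groups (207/207) and 0.67 with 5% cases. For an AUC against 0.5 (Hanley–McNeil variance), the same splits give 0.58 and 0.69. The figure fits many assumptions, and the point below does not depend on it.

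**Step 1: a two-marker rule from single-marker AUCs.** All inputs are assumed. Each marker is normal with SD 1 in cases and controls, oriented so that higher is more abnormal, with AUC 0.70. The case shift is then μ = √2 × z(0.70) = 0.742. The rule is positive if both markers exceed c (SDs above the control mean), and ρ is their correlation. Sensitivity = Φ₂(μ−c, μ−c; ρ) and specificity = 1 − Φ₂(−c, −c; ρ). For example, with ρ = 0 and c = 0.5, sensitivity = Φ(0.242)² = 0.355 and specificity = 1 − Φ(−0.5)² = 0.905.

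| c | ρ = 0 | ρ = 0.3 | ρ = 0.6 | ρ = 0.9 |
|---|---|---|---|---|
| 0 | 0.594 / 0.750 | 0.624 / 0.702 | 0.661 / 0.648 | 0.717 / 0.572 |
| 0.5 | 0.355 / 0.905 | 0.401 / 0.866 | 0.452 / 0.820 | 0.526 / 0.755 |
| 1.0 | 0.158 / 0.975 | 0.204 / 0.955 | 0.256 / 0.927 | 0.329 / 0.885 |

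Entries are sensitivity / specificity. Both AUCs are 0.70 in every cell. Only non-negative correlations are shown, because PG I is the numerator of I/II and positive dependence is the more plausible case.

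**Step 2: a rule abnormal at both ends.** Assume controls N(0, 1) and cases with the same mean and SD 2. By symmetry the AUC is exactly 0.50. The rule |x| > 1.5 nevertheless has sensitivity 2 × [1 − Φ(0.75)] = 45% and specificity 1 − 2 × [1 − Φ(1.5)] = 87%. A marker with this pattern would be reported as having no value.

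**Step 3: precision if scored directly.** Enrollment is 1490 (study design table). The number of neoplasms is not given, so prevalence is assumed. Clopper–Pearson 95% intervals for a sensitivity near 70%:

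- 2%: 30 cases, 21/30, 51–85%
- 5%: 74 cases, 52/74, 59–80%
- 10%: 149 cases, 104/149, 62–77%

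**Step 4: units.** The rule is in ng/mL. GastroPanel PG is listed in µg/L, which is numerically the same. Conventional PG is listed in mg/dL. Since 1 mg/dL = 10,000 ng/mL, 70 ng/mL = 0.007 mg/dL. The rule cannot be applied to the conventional values until the units are reconciled, and the document does not say for which assay the rule was set.

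**The case against.** The strongest reply is that the thresholds are not offered as neoplasm tests. The 70/3 rule serves only to define serological atrophy within naive status, and G-17 below 1 pmol/L is also an atrophy limit. Only the 0.5/4.7 pair is tied to cancer. The stated aim is to find levels for "detecting gastric neoplasms rather than focusing on identifying high-risk individuals", not to score imported limits. This stands in part: a reader might infer that 70/3 is the established neoplasm test and that the study fails to validate it, and the documents do not say so. The screening objective still makes its accuracy for neoplasm worth reporting.

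Second, a reader might infer that the study cannot state these error rates. That is not supported. PG I, PG II, their ratio, G-17 and histologically confirmed neoplasm status are all collected. McNemar's test and the search for blood levels both imply some dichotomised analysis. However, no cut-off, no way of choosing one and no performance measure is written down.

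Third, a reader might infer that scoring G-17 against neoplasm would test the remark about levels above 4.7 pmol/L. It would not: that remark concerns people without atrophy, not people without neoplasm.

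Fourth, the plan does not say outright that each ROC curve is for one marker. That is read from the endpoint list. An AUC for a combined model would still not give the accuracy of a fixed two-condition rule.

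**Conclusion.** The point holds as an omission from the analysis plan. AUC is the only accuracy measure named for a screening-validity objective, and it determines neither the joint pepsinogen rule nor a two-sided G-17 rule. It does not invalidate the planned analyses, and it can be put right with data in hand.

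The size cannot be fixed from the documents. Under the assumed model, sensitivity ranges from 0.16 to 0.72 and specificity from 0.57 to 0.98 with identical AUCs. Part of that spread comes from the choice of cut-off. At c = 0.5, correlation alone accounts for 17 points of sensitivity (0.355 to 0.526) and 15 points of specificity (0.905 to 0.755). The AUC of 0.70, the normal distributions, the correlations, the G-17 example and the case numbers are all assumptions.

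**What to change.** Add to the statistical section sensitivity and specificity with exact 95% CIs, for gastric neoplasm and for adenocarcinoma, overall and by *H. pylori* status, at cut-offs fixed in advance:

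- PG I ≤70 ng/mL and I/II ≤3, after stating which assay the rule belongs to and reconciling mg/dL with ng/mL.
- G-17 <0.5 or >4.7 pmol/L.
- Optionally G-17 <1 pmol/L, labelled as an atrophy rule.

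In the naive stratum the pepsinogen rule is negative by definition on the assay used to classify status. Its accuracy there should be marked as not estimable and not reported as a finding.

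Use McNemar's test only for paired binary results, within cases (sensitivity) and within controls (specificity) separately. Read any comparison of the two platforms at a shared cut-off as reflecting calibration as well as accuracy. Label cut-offs derived from this cohort as exploratory. State the number of neoplasms beside each estimate.

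The cost is one extra table from data already collected. The downside is that the existing rules may look less accurate than cut-offs fitted to this cohort, and intervals by *H. pylori* status will be wider than those in Step 3.

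### ROC curves are summarised by AUC but compared with McNemar's test, which does not test a difference in AUC

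*Combined protocol and SAP*

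**What the plan says.** Under 'Sample size and statistical analysis', the plan states that "receiver operating characteristic (ROC) curve analysis was done, and presented as area under the curve (AUC". The next sentence reads "ROC curves were compared using the McNemar's test". The significance rule is that "a p -value less than 0.05 was considered significant". No other part of the document names a method for comparing AUCs.

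The comparison is otherwise undescribed, and its parts have to be inferred:

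- **Outcome.** The primary endpoint concerns blood findings "indicating the presence of gastric neoplasms", and the section on additional features speaks of "detecting gastric neoplasms rather than focusing on identifying high-risk individuals". Gastric neoplasm is therefore the likely outcome, although the sentences just before the ROC text deal with severity of atrophy.
- **Pairs.** The Rationale says "We tried to identify significant variables using GastroPanel tests and traditional serum PG assays according to the presence gastric neoplasms", which points to GastroPanel against the conventional assays. G-17 is in the primary endpoint but has no conventional counterpart in the list of variables. The additional-features section leaves open whether G-17 improves on pepsinogen alone for finding neoplasms.
- **Cut-offs.** None is tied to the ROC comparison. The pepsinogen limits in the Rationale define "no serologically detected atrophy" as part of *H. pylori*-naive status. The G-17 values in the additional-features section are background from other studies.

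**The concern.** An AUC averages performance over all cut-offs. McNemar's test uses only discordant pairs of binary results, so each quantitative marker must first be cut into positive and negative. It then compares sensitivity (among cases), specificity (among controls) or accuracy (among all participants) at that single point. The result mixes how well the markers discriminate with where they were cut.

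A reader who sees two AUCs with a p-value will take it as a test of their difference. Depending on the cut-offs, McNemar's p-value can be small when the AUCs are equal and large when they differ. What is at stake is any statement that one assay or marker discriminates better than another.

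**Working it through.** **The plan's own figure.** There is none for this comparison. The stated power of 0.842 at 414 individuals comes without an effect size, test or prevalence and is not linked to ROC curves. It can be neither reproduced nor faulted here.

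**Inputs.** From the documents: N = 1,490 (enrolment, 'Study design') and two-sided 0.05 ("two-sided tests were used at a significance level of 0.05"). Assumed, because the documents give none: 75 neoplasms (range 30 to 150), within-group correlation 0.8 (range 0.6 to 0.8), AUCs of 0.70 and 0.78, and the cut-offs. With 75 neoplasms there are 1,490 − 75 = 1,415 controls.

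**Formulas.** The markers are normal with unit variance and shifted by μ in cases.

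- AUC = Φ(μ/√2), so μ = √2·Φ⁻¹(AUC): 0.742 for AUC 0.70 and 1.092 for AUC 0.78.
- The cut-off is c = Φ⁻¹(1 − false-positive rate), and sensitivity is Φ(μ − c).
- McNemar: (|b − c′| − 1)²/(b + c′), where b and c′ are the discordant counts; exact below 25 discordant pairs.
- DeLong: z = (AUC₁ − AUC₂)/SE, with the paired SE from placement values.

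**Scenario 1: equal AUCs of 0.70, cut-offs at 20% and 30% false positives.**

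- Sensitivities: Φ(0.742 − 0.842) = 46.0% and Φ(0.742 − 0.524) = 58.6%.
- Correct calls: 75 × 0.460 + 1,415 × 0.80 = 1,166.5 (78.3%) against 75 × 0.586 + 1,415 × 0.70 = 1,034.5 (69.4%).
- These differences are real, but they come only from the cut-offs.

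**Scenario 2: AUC 0.70 v 0.78, cut-offs solved for equal accuracy.**

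- Marker 1 at 20.0% false positives: 78.3% accuracy, as above.
- Marker 2 at 20.8% false positives: sensitivity Φ(1.092 − 0.814) = 61.0%; accuracy (75 × 0.610 + 1,415 × 0.792)/1,490 = 78.3%.

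**Scenario 3: both cut-offs at 20% false positives.** At AUC 0.78 sensitivity is Φ(1.092 − 0.842) = 59.9%, against 46.0% at AUC 0.70.

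**Simulated rejection rates (75 neoplasms, correlation 0.8)**

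| Scenario | McNemar, sensitivity | McNemar, accuracy | DeLong |
|---|---|---|---|
| 1. Equal AUCs, different cut-offs | about 58% | 100% | about 5% |
| 2. AUC 0.70 v 0.78, equal accuracy | 74% | about 4% | about 98% |
| 3a. AUC 0.70 v 0.78, matched cut-offs | 66% | 10% | about 99% |
| 3b. Equal AUCs, matched cut-offs | 2.6% | 4.5% | 5.2% |

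**Range over 30 to 150 neoplasms and correlation 0.6 to 0.8**

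- Scenario 1: McNemar on sensitivity 14% to 89%; DeLong about 5% to 6%.
- Scenario 2: McNemar on accuracy about 4% to 5% and on sensitivity about 17% to 99%; DeLong 50% to 100%.
- Scenario 3a: McNemar on sensitivity 16% to 94%; DeLong 49% to 100%.

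**What a paired AUC analysis would report.** At AUC 0.70 v 0.78 and correlation 0.8, the DeLong standard error is about 0.031, 0.020 and 0.014 for 30, 75 and 150 neoplasms. The 95% half-widths are 1.96 × SE, about ±0.06, ±0.04 and ±0.03. McNemar's test yields no such interval.

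**The only planned size, N = 414.** A separate simulation assumed 10% prevalence, correlation 0.5, both AUCs 0.70 and cut-offs at 0.5 and 1.0 SD. DeLong rejected 6.8%, and McNemar 46.8% among cases and 100% on overall positivity (500 runs, so a Monte Carlo error of about one percentage point near 5%).

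**The case against.** The strongest defence is that the authors meant to compare sensitivity or specificity at chosen cut-offs, for which McNemar's test is right. Scenario 3b shows it holds its level when false positives are matched. Scenario 2 shows it can pick up a true difference through sensitivity, nearly as often as DeLong with 150 neoplasms. This stands: McNemar's test is not invalid in itself. But the sentence says that curves are compared, straight after naming AUC as their summary, and no cut-offs are given for the purpose.

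It can also be said that the illustration uses fixed, chosen cut-offs, whereas the additional-features section suggests that cut-offs would be found from the data. That is fair, but it does not rescue the test. With Youden cut-offs taken from the same data (both AUCs 0.70, correlation 0.8, 30 to 150 neoplasms), McNemar rejected about 24% to 51% on sensitivity and 81% to 90% on accuracy.

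A reader might infer that the unstated outcome, pairs and cut-offs are a second error. In a plan this short they are missing detail. The primary endpoint and the logistic regression both point to gastric neoplasm.

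**Conclusion.** The sentence is wrong as written: the named test does not address the named summary. That conclusion rests on what McNemar's test computes and needs none of the assumed inputs. The rejection rates do depend on the assumed number of neoplasms, correlation, AUCs and cut-offs. They illustrate the direction and possible size of the problem and are not estimates for this study.

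A reader might infer that the study's main findings are undermined. The documents do not support that. No endpoint is an AUC difference; the primary endpoint is served by group tests and logistic regression. Those, and each marker's own AUC, do not depend on this sentence. The error is confined to the supporting comparison of markers, should be corrected before such a comparison is reported, and is cheap to correct.

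**What to change.** Replace the McNemar sentence with:

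> For gastric neoplasm, AUCs of markers measured in the same participants (GastroPanel v conventional *H. pylori* IgG, PG I, PG II and I/II ratio; and G-17 v the PG markers) will be compared with the DeLong test for correlated ROC curves or a paired bootstrap, reporting the AUC difference with 95% CI. The added value of G-17 to PG will be tested by a likelihood-ratio test in the logistic model, with a bootstrap CI for the AUC change, because the ordinary DeLong test is unreliable for nested fitted models. McNemar's test will be used only for sensitivity (in neoplasms) and specificity (in controls) at prespecified cut-offs; comparisons at cut-offs derived from the same data will be labelled exploratory.

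If the ROC comparison was meant for atrophy, name that outcome and use the same paired AUC method. It would also help to state whether p-values are adjusted for the number of pairs, and whether the comparison is repeated by neoplasm type or *H. pylori* status.

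The cost is a change of SAP wording and a different procedure on the same data, with no new participants or measurements.

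### The rationale raises whether gastrin-17 adds to pepsinogen, but the analysis plan does not specify the comparison that would answer it

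*Combined protocol and SAP*

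**What the plan says.** - **Rationale** (Additional features on the main concept of the study). G-17 is presented as what GastroPanel has and traditional pepsinogen assays lack. The section then says that "it is still uncertain whether adding a G-17 measurement to PG assays would contribute to the detection of gastric neoplasms". The aim drawn from this begins "Hence, we attempted to identify actual blood levels for" and concerns detecting neoplasms.
- **Objective and endpoint.** The primary objective is "To determine the validity of blood tests for gastric cancer screening". The primary endpoint is "Significant blood test findings (*H. pylori* IgG, PG I, PG II, I/II ratio, G-17) indicating the presence of gastric neoplasms", a list of markers one by one. Added value is not listed.
- **Data.** The initial visit includes "Blood test for *H. pylori* immunoglobulin G, pepsinogen, and gastrin-17 levels". A second set of measurements without G-17 is listed as "Conventional serum assays (Chorus tests and HBI PG assays").
- **Analysis** (Sample size and statistical analysis). Logistic regression is used to find independent variables for neoplasm. In addition, "receiver operating characteristic (ROC) curve analysis was done, and presented as area under the curve (AUC"), and the ROC curves are compared by McNemar's test. The covariates, the order of models and the curves compared are not given.

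**The concern.** Whether G-17 helps once pepsinogen is known is a question about two nested predictors in the same people. No analysis in the plan is described that way. What each listed analysis would deliver:

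- A G-17 curve alone shows what G-17 does alone, not what it adds.
- An adjusted G-17 odds ratio addresses independent association, provided pepsinogen is in the model. It does not give the gain in detection.
- McNemar's test compares paired positive/negative calls at chosen cut-offs. It does not test a difference in AUC.
- A contrast of GastroPanel with the conventional kits would mix G-17 with differences in the pepsinogen and IgG assays.

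At stake is the conclusion about the marker that distinguishes GastroPanel. As written, it would depend on model and curve choices made after the data are seen.

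**Working it through.** **The plan's own figure.** The stated power is 0.842 with 414 individuals, two-sided 0.05. It cannot be reproduced, because no effect size, case share or test is given. It is tied to validating GastroPanel, not to the added value of G-17, so it does not bear on this point.

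**Do single-marker AUCs determine the gain?** The AUCs and correlations here are assumptions; the documents give none. Take an equal-variance binormal model with within-group correlation ρ:

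- d = √2·Φ⁻¹(AUC)
- D² = (d₁² + d₂² − 2ρd₁d₂)/(1 − ρ²)
- combined AUC = Φ(D/√2)
- adjusted log odds ratio for G-17 per SD = (d₂ − ρd₁)/(1 − ρ²)

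Pepsinogen AUC 0.65 gives d₁ = 0.5449, and G-17 AUC 0.60 gives d₂ = 0.3583. So d₁² + d₂² = 0.2969 + 0.1284 = 0.4253, and d₁d₂ = 0.1952.

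| ρ | D² | Combined AUC | Gain | Adjusted G-17 OR per SD |
|---|---|---|---|---|
| +0.66 | (0.4253 − 0.2577)/0.5644 = 0.297 | 0.650 | 0.000 | 1.00 |
| 0 | 0.4253 | 0.678 | 0.028 | 1.43 |
| −0.3 | (0.4253 + 0.1171)/0.91 = 0.596 | 0.707 | 0.057 | 1.77 |

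With AUCs of 0.70 and 0.50, d₁ = 0.7416 and d₂ = 0, so D² = 0.550/(1 − ρ²).

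- ρ = 0.3: combined AUC 0.709, gain 0.009, adjusted OR 0.78.
- ρ = 0.5: combined AUC 0.728, gain 0.028, adjusted OR 0.61.

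So the same single-marker AUCs fit both no gain and a useful gain. The last column shows that a model holding both markers does tell these cases apart. The ambiguity arises only if the conclusion rests on single-marker curves.

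**Shape of G-17.** The closing section cites a study linking cancer to G-17 both below 0.5 and above 4.7 pmol/L. With such a relation, a curve on raw G-17 can sit near 0.5 although the marker carries information, and a linear logistic term can miss it too.

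**How precisely could the gain be estimated?** Enrolment is 1490; the number of cases is not given. Assume a pepsinogen AUC of 0.65, a correlation r between the two AUC estimates of 0.6 to 0.9, and neoplasms in 3% to 20%. The Hanley–McNeil variance is

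V(A) = [A(1−A) + (n₁−1)(A/(2−A) − A²) + (n₀−1)(2A²/(1+A) − A²)]/(n₁n₀).

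Example with 10% cases (n₁ = 149, n₀ = 1341) and r = 0.8:

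- V(0.65) = 0.000646 and V(0.70) = 0.000617.
- SE of the difference = √(0.000646 + 0.000617 − 2×0.8×√(0.000646×0.000617)) = 0.0159.
- Power = Φ(0.05/0.0159 − 1.96) = 0.88.

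Over the whole range, power for 0.65 versus 0.70 runs from 0.24 to above 0.99. For 0.65 versus 0.67 it runs from 0.07 to 0.67.

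**The case against.** The strongest reply has three parts.

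1. **Added value is not an objective.** The sentence about G-17 closes a literature paragraph, and the objective and endpoints do not mention incremental value. This stands: no listed endpoint goes unanalysed. But the aim is introduced as following from that uncertainty, and G-17 is in the primary endpoint, so a reader will look for an answer.
2. **The planned regression may already answer it.** If pepsinogen and G-17 enter together, the Wald test of the G-17 coefficient is asymptotically equivalent to a likelihood-ratio test, and the odds ratios above follow the gains. This also stands, conditionally. The plan does not say that they enter together or in what form, and an odds ratio still does not state the gain in detection.
3. **The kit contrast is conjecture.** The expected result, that "GastroPanel test and conventional serum pepsinogen findings would differ according to the presence and types of gastric neoplasms", contrasts patients rather than kits. Nothing says that a kit difference will be read as evidence on G-17. That is right; the point is only that such a difference could not serve as that evidence.

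A reader might infer that the study cannot answer the question at all. The documents do not support that: both markers come from the same participants, and the curves compared are unnamed rather than known to be single-marker.

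**Conclusion.** The point holds as a gap in specification with a cheap, better method available. The rationale turns on what G-17 adds to pepsinogen, and the plan neither assures a model containing both nor measures the gain in AUC. The one ROC comparison it names uses a test that does not compare AUCs.

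The range of 0.000 to 0.057 is illustrative and rests on assumed AUCs, correlations and binormality, with pepsinogen alone as the baseline. It shows that single-marker AUCs do not determine added value. It should not be read as a forecast for this study, or as showing that a joint logistic model would miss the effect. The primary objective is not invalidated.

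**What to change.** In the statistical analysis section, specify the following within the GastroPanel data and in the same participants:

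- **Model A:** age, sex, PG I and PG I/II ratio.
- **Model B:** model A plus G-17 entered non-linearly, with the form fixed in advance.
- **Report:** the likelihood-ratio test of B against A, and the paired AUC difference with an optimism-corrected bootstrap 95% CI. Use these in place of McNemar's test for AUCs.
- **Interpretation:** base any statement on G-17's contribution on this comparison, not on differences between GastroPanel and the conventional kits. State the number of neoplasm cases beside the interval.

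The cost is one extra model pair on data already collected, plus a few lines of text. The downside is that the interval may be wide or include zero; it should then be reported as inconclusive rather than as proof that G-17 adds nothing.
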